14.0 Withdrawal of Subjects

- 14.1 Circumstances under which participants will be withdrawn from the research without their consent include significant cognitive impairment, psychosis, and/or imminent suicidal risk.
- 14.2 In the event of withdrawal, the study staff will debrief the participant, provide mental health resources if needed, and provide guidance for safely discontinuing participation (e.g., closing out their application account) and instructions for returning any study-provided materials (e.g., Fitbit devices).
- 14.3 When a participant withdraws from research, they may request their data to be deleted. Compensation will be provided based on completed study assessments; they will not be compensated for the study components that are incomplete. For participants who partially withdraw with continued data collection, only agreed-upon assessments (e.g., only EMAs) will continue to be used to gather data on study experience, acceptability, and feasibility. If they partially withdraw before the exit interviews are conducted, they will still be contacted and be invited to participate in the exit interview.

15.0 Risks to Subjects

- 15.1 Meditation-related risks: The National Center for Complementary and Integrative Health (NCCIH) states that meditation is generally safe for healthy people, but that adverse effects have also been reported. More common, less serious side effects that have been reported by individuals within the context of MBIs or of individuals who are meditating less than an

hour per day include: increased depression, anxiety or panic, re-experiencing of traumatic memories, dissociation, executive dysfunction, headaches/body pain and insomnia. A few case reports of more serious side effects including mania, psychosis, and suicidality have been reported, mostly in the contexts of intensive retreats (>5 hrs/day) or in conjunction with pre-existing psychopathology. The frequency of serious adverse effects in the context of MBIs is estimated to be less than 1%, although adequate estimates are not available.

Psychological distress: Research subjects participating in this study may experience possible psychological distress caused by questions asked during the in-person and online questionnaires that bring up painful memories or feelings. However, the resulting potential for injury to research subjects is judged to be minimal. With regard to psychological distress from taking part in the intervention, given that screening questions will exclude participants with substantial mental illness, and given the NCCIH statement above that “meditation is considered to be safe for healthy people,” we expect that the risk will be low.

Loss of confidentiality: Confidentiality will be maintained by using deidentified data sets. All electronic data files containing identifying information will be encrypted with cloud-based software. Although these measures have been taken to protect participants’ personal information and the likelihood of loss of confidentiality is minimal, complete confidentiality cannot be guaranteed when transmitting information over the internet. All information obtained from participants will be accessible only to research staff.

Risks Related to Wearable Devices: Wearing the Fitbit device may cause minor physical discomfort (e.g., skin irritation) or inconvenience in daily routines.

Oversight of internal monitoring of the participants’ safety will be conducted by the PI, [name], who is a licensed psychologist.

15.2 N/A

15.3 N/A

15.4 N/A

16.0 Potential Benefits to Subjects

16.1 Potential benefits from participating in the research include (a) increased awareness of daily mood, stressors, and present experience through EMAs; (b) development of a personal mindfulness meditation practice, which may help participants develop healthy coping strategies, improve emotion regulation, and reduce stress; and (c) practice of identifying and attempting behavioral change, which may lead to improvements in mental health indicators such as anxiety, depression, and loneliness. While the magnitude and duration of these benefits may vary by individual, participation offers the opportunity for personalized insight into their own behavioral and emotional patterns as well as skill-building.

16.2 N/A

17.0 Data Management and Confidentiality

17.1 Quantitative data will be analyzed using a combination of descriptive and inferential statistics. Feasibility and acceptability data (e.g., CSQ-8 and SEF scores, proportion of completed EMA prompts, engagement metrics such as weekly practice rates and frequency of practice use) will be summarized using means and standard deviations. Preliminary effects on other primary, secondary, and exploratory outcomes (e.g., depression, anxiety, sleep quality, emotion regulation, mindfulness) will be evaluated using repeated measures analyses, such as mixed-effects models, to characterize effect sizes (e.g., Cohen's *d*). We will use mixed-effects modeling with time as fixed effect and participant as random effect to model trajectories, incorporating baseline covariates, to account for within-subject correlations across time points. EMA data will be analyzed using mixed-effects models to assess within-person day-to-day associations between stress and intervention engagement.

Qualitative exit interview data will be transcribed using Dedoose, deidentified, and analyzed using thematic analysis. Framework analysis, a structured qualitative analysis method, will be used. We will follow a standard procedure, including (1) data familiarization, (2) deductive coding based on relevant research questions and inductive coding emerging from the data, (3) development of a framework of codes specific to intervention messages and content, (4) organization of relevant codes into themes, and (5) integration and interpretation of the themes to provide meaning and explanation for the results. Multiple coders will be involved in the data analysis process to ensure analyst triangulation and rigor. We will follow best practices on enhancing rigor of qualitative research, adhere to reporting standards outlined by the American Psychological Association, and demonstrate trustworthiness (credibility, transferability, dependability, and confirmability). Voice recording data will similarly be transcribed automatically through Expiwell's AWS and be verified/deidentified before analysis. Natural language processing will be used for the deidentified transcripts of the voice recordings, for example, to run sentiment analysis to examine changes in participant's emotions over time. To mitigate the risk of recording third-party participant voices, participants in the study will be instructed to complete the voice recording in a private location and to ensure no other individuals are present or speaking during the recording. Participants will be reminded to pause, stop, or restart the recording if another person enters the space.

17.2 Access to documents and records produced with study data will be limited to the PIs, project managers, research coordinators, and other related research personnel. All personnel involved will be required to sign confidentiality agreements and strict confidentiality will be maintained. Files with personal identifiable information (e.g., password-protected file linking PID to participant name, signed informed consent forms, interview recordings, and voice recordings) will be kept in closed network servers (i.e., Brown Stronghold) that only research staff have access to. Specifically for exit interview recordings, the interview will be recorded using the native recording feature on the Zoom platform (i.e., capturing both video and audio recording) and saved to the interviewer's Brown Zoom cloud. The RA

recording the interview will ensure that the setting “Allow cloud recording sharing” is disabled on Zoom. By disabling this setting, nobody other than the person who made the recording will be able to access that recording on the cloud. Therefore, the recording saved to the interviewer’s Brown Zoom cloud will be only accessible to the interviewer creating the recording. An audio-only recording file will then be downloaded from the Zoom cloud to Stronghold, and the original recording will be deleted from the Brown Zoom cloud.

- 17.3 Data will be monitored regularly for accuracy and cleaned according to set protocols. Standardized protocols will be followed by research staff for all data collection procedures, and regular audits will be conducted. All research staff will be trained in consistent data handling and confidentiality procedures.
- 17.4 The crosswalk files linking personally identifiable information (e.g., name, contact information) to PID will be stored separately from study data in encrypted, password-protected files and will remain there until either a manuscript utilizing the data is submitted for publication or for a period of 5 years after study completion (whichever comes first), consistent with institutional policy. This allows for the deletion of a participant’s data upon request, at any time prior to dissemination. The same will be applied to the contact information of participants who consent to being contacted about future research studies in the lab--their contact information (not linked to PID) will be retained for up to 5 years, after which point we will destroy the information. All de-identified study data, including survey responses, EMA data (including transcripts of the voice recordings), passive data from wearable devices, and exit interview transcripts, will be linked to a unique PID. De-identified data will be stored on secure, HIPAA-compliant servers at the Brown University School of Public Health indefinitely after the completion of the study. Access to data with personally identifiable information will be restricted to authorized study personnel, including the principal investigator and designated research staff, who are responsible for receipt and storage of data. The de-identified data can be shared with other researchers upon request after signing data confidentiality agreement; this process will be handled by the PI.

18.0 Provisions to Monitor the Data to Ensure the Safety of Subjects

- 18.1 Data collected in this study regarding potential suicidality will be evaluated at each timepoint (i.e., Zoom Screening Interview, T1, T2, and T3) to ensure the safety of participants. Specifically, we will review results of the MINI-Major Depressive Episode module, including participant response for question A3.g in the MINI-Major Depressive Episode module: “Did you repeatedly think about death (fear of dying does not count here), or have any thoughts of killing yourself, or have any intent or plan to kill yourself? Did you attempt suicide?”

The MINI-Major Depressive Episode module will be administered verbally by a research staff conducting the assessment on Zoom call (Refer to Section 6.2 for more details). At any time point, [name] will be notified of participants who have current Major Depressive Episode according to the module. At screening, if they screen positive they will be provided with

resources and excluded. while those who have current Major Depressive Episode at T1, T2, or T3 assessments will be provided with local mental health resources after the assessment is completed without being excluded from the study (refer to “MINI – Major Depressive Episode Referral Plan.docx”).

Further, as described in “Compiled Measures_GEM.docx”, for any participant saying Yes to question A3.g in the MINI-Major Depressive Episode module, the suicide safety and assessment plan will be automatically triggered through Qualtrics by redirecting the RA to a message telling them to stop assessment and administer the safety and assessment plan (refer to document named “Suicide Safety Plan_GEM.docx”). Because all eligible participants at this point will have only mild to moderately severe symptoms of depression (individuals with severe symptoms are screened ineligible at the Qualtrics screener survey), there is low likelihood that a participant will be at imminent risk of suicide; however, the suicide safety assessment and plan has been developed out of an abundance of caution. The Suicide Safety Assessment and Plan will be conducted by [name], a licensed psychologist and the principal investigator of the study, or by a study team member who has been formally trained by [name] and operates under her direct supervision and oversight, consistent with existing clinical trial protocols for NIH-funded studies in the lab. All study personnel will receive training from [name] on identifying and responding to suicide risk. In addition, [name] will be on-call and will be notified immediately of any safety concerns. Participants who have active suicide ideation according to the suicide safety assessment will be excluded from the study, and study staff will take actions according to the suicide assessment and safety plan (please refer to “Suicide Safety Plan_GEM.docx”).

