The post-intervention assessment (T2) will take place 1-2 weeks after the recommended modules are completed and include a total of 26 scales, measuring depression, anxiety, PTSD, functional impairment due to depression, functional impairment due to anxiety, interoceptive awareness, Major Depressive Episode, Generalized Anxiety Disorder, de-centering, rumination/perseverative thinking, theories of psychological distress, theories of emotion, internalized stigma, emotion regulation, loneliness, mindfulness, self-compassion, perceived stress, political stress, sleep, phone use, applied mindfulness process, overall well-being, client satisfaction, session evaluation, and adverse effects. The post-intervention assessment will take a total of 60-90 minutes.

Additionally at T2, participants will be invited to complete an exit interview via Zoom, the University approved web conferencing platform. Interview will take 90-120 minutes. In line with previous studies from our team, the interview will be recorded using the native recording feature on the Zoom platform (i.e., capturing both video and audio recording) and saved to the interviewer's Brown Zoom cloud. The RA recording the interview will ensure that the setting "Allow cloud recording sharing" is disabled on

Zoom. By disabling this setting, nobody other than the person who made the recording will be able to access that recording on the cloud. Therefore the recording saved to the interviewer's Brown Zoom cloud will be only accessible to the interviewer creating the recording. An audio-only recording file will be downloaded from the Zoom cloud to Stronghold, and the original recording will be deleted from the Brown Zoom cloud.

At follow-up assessment (T3), which will take place 3 months after the baseline assessment, we will include a total of 21 scales, measuring depression, anxiety, PTSD, functional impairment due to depression, functional impairment due to anxiety, Major Depressive Episode, Generalized Anxiety Disorder, interoceptive awareness, de-centering, rumination/perseverative thinking, theories of psychological distress, theories of emotion, internalized stigma, emotion regulation, loneliness, mindfulness, self-compassion, perceived stress, political stress, sleep, phone use, applied mindfulness process, and overall well-being. The follow-up assessment will take a total of 60-90 minutes.

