In addition to the weekly modules, participants will take part in a weekly, 1-hour "Group practice and connect" session on Zoom. The online sessions will comprise a cohort of 5-10 participants (depending on recruitment) and will be led by a research assistant, who has previous experiences with mindfulness programs as well as lived experiences of early life adversity. During each session, participants will be invited to participate in a group practice and reflection and to join group discussions on experiences regarding past week's practice. In the contact form (which is completed after the consent form), participants will be presented with the day and time of weekly sessions for the next two cohorts and asked to choose the times they are available for. If the participant is not available for either of the offered times, they will be marked as "deferred enrollment" in our participant tracking spreadsheet. A study RA will follow up with information about future cohort scheduling as that information becomes available.

Ecological momentary assessments and interventions: Over the first 4 weeks of the intervention period (i.e., Recommended Modules), participants will also complete 3 EMAs + EMIs per day through Expiwell. EMA and EMI will be delivered concurrently; the EMA will collect participant's response on their current mood, recent stressful experience, and type of stressor; participants will then receive a list of mindfulness exercises, which will be tailored to the type of stressor/emotion they will have indicated. The last EMA of the day will also include an option for the participants to submit a voice recording, serving as a "daily journal" at the end of the day to understand participant's daily experiences, including daily stressors and mindfulness practice application. To mitigate the risk of recording third-party participant voices, participants in the study will be

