instructed to complete the voice recording in a private location and to ensure no other individuals are present or speaking during the recording. Participants will be reminded to pause, stop, or restart the recording if another person enters the space. Participants will also be reminded that the voice recording is optional--they may skip voice recording submission without penalty and still receive compensation. Audio will be downloaded from Expiwell, uploaded to Stronghold, then deleted from Expiwell's storage. The audio housed in Stronghold will be deleted after they are transcribed and vetted for accuracy by study staff. A research assistant will monitor responses to the EMA on a daily basis (including the voice recording, where a transcript will automatically become available through Expiwell's AWS service). Any reportable events that are observed will be reported to the PI, and the PI will be available to meet, if necessary, to review concerns regarding a particular participant or any problems that may arise for participants.

Weekly assessments: During first 4 weeks of intervention period (i.e., Recommended Modules), participants will be asked to complete a survey every week. The survey consists of 2 scales (PHQ-9 and GAD-7) as well as 3 items from interoceptive awareness scale, 3 items from de-centering scale, 3 items from perseverative thinking scale, and 1 item from theory of distress scale. Each survey will take 4-5 minutes, with a total of 16-20 minutes over the 4 week period.

Wearable device: Also during the first 4 weeks of intervention period (i.e., Recommended Modules), data will be collected from a Fitbit from each participant. Data collected include total sleep time, sleep onset latency, REM and non-REM sleep duration, sleep/wake variability, and resting heart rate. Each participant will be mailed a Fitbit from the study team along with a pre-paid return envelope at the enrollment in the study. These devices will be assigned to participants and linked to de-identified study accounts only. Participants will be instructed to wear the Fitbit device daily, before going to bed, for the entire 4-week period. At the end of the intervention, participants will be asked to return the Fitbit using the pre-paid return envelope.

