Self-report data on feasibility, acceptability, and preliminary efficacy: Data on feasibility and acceptability as well as preliminary efficacy of the intervention on study outcomes (including mental health, functional impairment, emotion regulation, loneliness, mindfulness, self-compassion, stress, sleep, phone use, overall well-being, etc. – refer to Section 6.2 for full list of scales measured at each time point) will be collected via Qualtrics at baseline, post-intervention, 3-month follow-up, and weekly assessments during the first 4 weeks of intervention period (i.e., Recommended Modules).

EMAs: Daily self-reports on stress, mood, and emotional states will be collected on the Expiwell application. Furthermore, voice recordings for a "daily journal" will be collected during the last EMA of the day. Participants will be reminded that the voice recording is optional--they may skip voice recording submission without penalty and still receive compensation.

App engagement metrics: Frequency and duration of EMI-triggered and self-initiated mindfulness practice sessions will be collected on Expiwell.

Sleep metrics: Continuous objective data on sleep metrics (e.g., sleep latency, REM/non-REM sleep, sleep fragmentation, total sleep time, sleep efficiency) will be collected using wearable devices (i.e., Fitbits).

Semi-structured interviews: Qualitative feedback on intervention experience, feasibility, acceptability, and suggestions for improvement will be collected through a semi-structured Zoom interview with an RA.

6.5 Participants will complete a 3-month post-baseline follow-up survey after the 4-6-week intervention (4 weeks recommended, 2 weeks optional/bonus). Similarly to post-intervention survey, this assessment will collect self-report data on mental health, functional impairment, emotion regulation, loneliness, mindfulness, self-compassion, stress, sleep, phone use, overall well-being, etc. (refer to Section 6.2 for full list of scales measured 3-month follow-up).

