10.0 Inclusion and Exclusion Criteria

- 10.1 Screening survey: Individuals interested in the study will access a Qualtrics survey via recruitment links. The survey will be developed based on the study's inclusion and exclusion criteria (except for imminent risk of suicide and current Major Depressive Episode, which will be assessed during the Zoom screening interview). Scores on screening measures within the survey will be calculated in real time using Qualtrics' scoring feature—if a potential participant's score meets the study's inclusion threshold (see section 10.2), the survey flow will set an embedded variable ("eligible") to true; otherwise, it will be set to false. Statement addressing the legal concerns of underage consumption of alcohol and illegal substance use has been added to the screener.

Individuals who meet the eligibility criteria will be redirected to a separate Qualtrics form where they can review the Informed Consent Form (ICF) and complete a contact form, which will collect their full name and email address. These individuals will also be asked if they would like to be notified for future research. Please refer to the document named "Compiled measures_GEM.docx" for the screening survey, contact form, and future contact form. A trained research staff will then follow up with the eligible participants to schedule a Zoom-based screening interview.

Zoom screening interview: The interview will take 15-30 minutes to complete and will serve the following purposes: (a) confirm participant eligibility and identity by participant showing any form of ID including photo, name, and age; (b) review informed consent form; (c) review study procedures and answer any questions the participant may have; (d), screen for current Major Depressive Episode and imminent risk of suicide; and (e) inform the participant (if eligible and interested to enroll) of the next steps, which includes the next Zoom call meeting for baseline assessment and onboarding (refer to section 6.2). At the beginning of the screening call, RA will remind participants that if they disclose information indicating imminent risk of serious harm to themselves or others, this information must be reported to relevant law enforcement or other authorities. The RA conducting this interview will use a Qualtrics survey with the questions/measures that need to be administered (e.g., the MINI-Major

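### The weekly PHQ-9 and GAD-7 collected in Weeks 1-4 have no stated safety reviewer, cut-off or action; a flag at PHQ-9 of 20 or more would be a cheap addition

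*Protocol*

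**What the plan says.** Protocol section 18.1 says that data on potential suicidality "will be evaluated at each timepoint (i.e., Zoom Screening Interview, T1, T2, and T3"). It names one instrument: "Specifically, we will review results of the MINI-Major Depressive Episode module", including its item on thoughts of death and suicide. A positive module leads to notification of the psychologist who is principal investigator, and to referral. A positive suicide item triggers the suicide safety plan.

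Section 6.2 adds a weekly survey in the first four weeks of the intervention: "The survey consists of 2 scales (PHQ-9 and GAD-7"), plus a few mechanism items. Section 6.4 says that the self-report outcome data "will be collected via Qualtrics at baseline, post-intervention, 3-month follow-up, and weekly assessments", so the weekly scores sit in the same system as the main surveys. The SAP names the PHQ-9 and GAD-7 only as clinical outcomes.

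Several other safeguards operate during those weeks:

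- Under 6.2, "A research assistant will monitor responses to the EMA on a daily basis", and reportable events go to the principal investigator.
- Weekly group sessions take place "and will be led by a research assistant" (6.2).
- Participants are encouraged to tell staff about increased distress (6.2).
- Withdrawal brings a debrief and resources (14.2).
- The principal investigator oversees safety (15.1, 25.1).
- A psychologist is on call (18.1).

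**The concern.** The weekly PHQ-9 is the only depression scale described between T1 and T2, and the supplied text gives it no safety use. That matters for three reasons drawn from the protocol itself:

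- Section 15.1 lists worsening depression and anxiety among the more common reported effects of meditation, and 4.2 commits the study to monitoring negative effects.
- Participants must not be in mental health treatment at entry (10.2), so an outside clinician is less likely to notice a decline.
- The statement that imminent suicide risk is unlikely (6.2, 10.1, 18.1) gives as its reason that severe symptoms were screened out at the screener. A weekly PHQ-9 of 20 or more would mean that this reason no longer holds for that participant.

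At stake is a delay in noticing a severe score that the study already holds. No endpoint, power figure or efficacy conclusion is affected.

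**Working it through.** No figure in the plan needs reproducing. The check has three parts.

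**1. Review points against data collected**

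| Time | Data | Safety review stated |
|---|---|---|
| Screening interview, T1, T2, T3 | MINI depressive episode module | Yes: 18.1, with notification, referral and safety plan |
| Weeks 1-4, daily | EMA responses and optional voice journal | Yes: 6.2, read daily, reportable events to the principal investigator, no score threshold |
| Weeks 1-4, weekly | PHQ-9 and GAD-7 | None found |

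The regular data monitoring in 17.3 is for accuracy, so it does not fill the third row.

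**2. Volume and delay**

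- Forms: 44 participants (12.1) x 4 weekly surveys (6.2) = 176. If only the 35 completers in 12.2 are counted, 35 x 4 = 140.
- T2 "will take place 1-2 weeks after the recommended modules are completed" (6.2). Assume each survey is done at the end of its week.
- Week 4 form: 1-2 weeks to T2.
- Week 1 form: 3 + (1 to 2) = 4-5 weeks to T2.

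**3. Cost of a flag at PHQ-9 of 20 or more, when nobody truly changes**

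The documents give no PHQ-9 mean, SD or correlation over time, so these are assumptions. Each simulated participant has one entry score and four weekly scores, equally correlated (r), rounded and limited to 0-27. Only those with an entry score of 5-19 are kept. This follows the statement in 18.1 that severe scores are screened out. There were 400,000 simulated participants, with an assumed mean of 10.

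| SD | r | P(any weekly score of 20 or more) | Participants of 44 | Forms of 176 |
|---|---|---|---|---|
| 4 | 0.85 | 0.015 | 0.7 | 1.0 |
| 4 | 0.60 | 0.026 | 1.2 | 1.4 |
| 5 | 0.85 | 0.043 | 1.9 | 2.9 |
| 5 | 0.60 | 0.078 | 3.4 | 4.5 |

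Participants = 44 x P, using unrounded probabilities. A repeat of the simulation agreed to within simulation error.

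Sensitivity, over the same SDs and correlations:

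- Mean 8: 0.2-1.7 of 44.
- Mean 12: 1.8-6.4 of 44.
- Mean 10, with entry on GAD-7 alone admitting PHQ-9 scores of 0-4: 0.6-3.0 of 44.

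A change rule was also considered: a 5-point rise from T1 on either scale. With a GAD-7 mean of 9, SD of 3.6-4.5 and cross-scale correlation of 0-0.7 (all assumed), it would falsely flag about 3-24 of 44. That is why only an absolute PHQ-9 cut-off is proposed.

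**The case against.** The strongest reply is that the gap may not exist. Section 18.1 refers to the Compiled Measures file for its Qualtrics trigger and to a separate Suicide Safety Plan, and neither was available. A weekly rule could sit in one of them. This stands, so the claim is limited to the protocol and SAP as supplied.

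Second, protection is broader than one screening score. Section 10.2 excludes imminent suicide risk, a current diagnosis of major depressive disorder and a MINI-defined episode; the MINI is repeated at T1; all personnel are trained to recognise suicide risk; and mood is sampled three times a day and read daily. This lowers the risk. But the entry and T1 checks precede Weeks 1-4, and EMA escalation has no threshold. The SAP's EMA benchmark can be met with just over half of participants completing 50% of prompts, so considerable non-response is tolerated.

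Third, the benefit is unquantified. The simulation prices false flags only, on assumed inputs, and does not model the MINI exclusions. This is correct: the frequency of true worsening cannot be derived from the documents.

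Fourth, the flag is partial. It would miss suicidality at lower totals and does nothing with the GAD-7. It also needs more than a score: no staff member is described as present for the weekly survey, so a flagged participant must be identified from the study number and contacted. These are fair limits, but that step uses the existing crosswalk file and existing staff.

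**Conclusion.** The concern holds as an improvement to safety monitoring that the sponsor should make. It does not show an error of calculation or a contradiction in the plan. Section 18.1 does not list the weekly survey, and neither supplied document assigns its up to 176 forms a reviewer, cut-off or action. A severe score missed by the other routes could wait about 1-5 weeks for the next scheduled review, assuming end-of-week completion.

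The cost conclusion rests on assumed PHQ-9 distributions: roughly 1-3 of 44 participants flagged without true change in the central case, and 0.2-6.4 across means of 8-12. The load is small throughout. Confidence is medium, because a weekly rule may exist in files not supplied.

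**What to change.** Add the weekly survey to 18.1 as a review point. Score the PHQ-9 automatically in Qualtrics; section 10.1 already says of the screener that "Scores on screening measures within the survey will be calculated in real time". Notify the on-call psychologist of any weekly PHQ-9 of 20 or more, and state how soon the score is read and who contacts the participant. The psychologist then decides whether the existing referral plan or suicide safety plan applies, because 18.1 keys those plans to the MINI. Report the number of participants flagged.

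No GAD-7 or change-from-T1 trigger is proposed; a sentence giving the reason would be useful. If the Compiled Measures file or the Suicide Safety Plan already contains a weekly trigger, cite it in 18.1 instead.

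The cost is a short addition to 18.1, a survey alert, and a little on-call time for about 1-3 false flags (up to about 6 if the mean PHQ-9 is 12). It needs no new software, role or data collection.
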